9. STATISTICAL CONSIDERATIONS

9.1. General Design Issues

In the proposed single-arm phase II trial, we define favorable impact on the neurocognitive outcome as at least 0.5 standard deviation (SD) improvement in performance on attention measures (measured as described above) after administration of C7. That is, impact on the outcome is determined by whether a treatment causes at least 0.5 SD improvement on the primary attention measure for that age group in a single arm trial and the interest is **primarily focused on reaching a decision on whether to progress with C7 to a future larger trial**. (Note: The SD is a normative parameter provided with the testing instruments). The evidence to make this decision is evaluated by testing the null hypothesis that the true efficacy rate is less than or equal to some pre-specified value. It is desirable to achieve this goal whilst minimizing the number of subjects exposed to a novel agent. Here, we use the Simon's optimal two-stage design that yields the smallest expected sample size when the null hypothesis is true.

We apply Simon's optimal two-stage design (24) using as primary outcome attention performance for each of three age groups. At least 0.5 SD improvement in performance on the primary attention measure after the administration of C7 is considered a favorable outcome. The measurement of 0.5 SD improvement is commonly accepted as the cutoff for a minimally clinically important difference, as described in various studies (e.g., 32, 33).

This protocol will yield data that allow a clear **go/ no-go decision** regarding whether C7 should proceed to an efficacy trial:

- If a favorable outcome occurs in less than 50% of subjects, we will recommend that C7 not proceed to an efficacy trial.
- If a favorable outcome occurs in at least 80% of subjects, we will recommend that C7 proceed to an efficacy trial.

The sample size estimation for this optimal two-stage design is given in Section 9.3.

If an intermediate number of subjects (51 – 79%) exhibit a favorable primary attention outcome, the rest of outcomes, including the long-term, 6-month responses, will be considered for the go/ no-go decision on the basis of impact on these outcomes and the disease process, in addition to tolerability and safety indicators.

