Clinical significance and meaningfulness of the secondary EEG outcome: A specific (but variable across studies) percentage in EEG seizure reduction is a generally accepted outcome in epilepsy trials. The spike-wave and other EEG changes investigated above in this trial have the potential to reflect a meaningful disease burden reduction to patients that would be associated, if realized, with considerably fewer observable seizures, since EEG seizures are significantly more frequent than overt seizures in G1D (1). In this publication (1) we observed that, on average, a reduction in seizure rate comparable to the reduction sought above is associated with a significant acute (hours to days) impact on neuropsychological performance as well as sustained (months) quality of life and neuropsychological scores (1). As described in the proposal, this rate allowed many patients to significantly increase school performance, social interactions, autonomy and a decrease in or a cessation of antiseizure drugs. Every patient who participated in (1) experienced improvement in terms of one or more of these aspects and most improved in all of them. Thus, the expected reduction in EEG spike-wave burden after C7 treatment may be highly medically significant, but the definitive implications of this will be established only in more advance-phase trials. Therefore, we will attempt to relate attention scores (primary outcome) with EEG recordings (used here as a surrogate marker of the disease and a secondary outcome) to seek such correlations. The long-term aspects of the treatment, which may be expected to illustrate sustained or additional benefits as in (1) are also captured on the 6-month on-treatment study design.

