9.2. Outcomes

9.2.1. Primary outcome

9.2.1.1. Attention performance

C7 provides a spectrum of short-term (hours to days) and long-term (over 6 months) benefits in subjects with G1D as measured by a 0.5 SD improvement in performance on the primary attention measure both in the acute and long-term.

Subjects receiving C7 supplementation will experience a significant (0.5 SD) improvement in performance on the primary attention measure for each subject's age group.

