9.2.2. Secondary outcomes

9.2.2.1. EEG

C7 provides a spectrum of short-term (hours to days) and long-term (over 6 months) benefits in subjects with G1D as measured by a decrease in abnormal EEG activities as defined above both in the acute and long-term.

9.2.2.2. Other neuropsychological and neurological performance, such as ataxia.

Subjects undergoing C7 supplementation will experience improvements in neuropsychological and neurological performance over the long term. Subjects will experience an increase in vocabulary expression and recall in both the acute (days) and long term (months) time frames. Subjects will also experience decreases in ataxia and other neurological symptoms measured on the neurological assessment.

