9.5. Data Analyses

Summary descriptive statistics: For normally distributed, continuous data, means and standard deviations will be used to describe the demographic and clinical characteristics of the patient population participating in the study and medians and semi-interquartile ranges will be used to describe characteristics of the patient population when the data are continuous, non-normally distributed. For categorical or dichotomous variables, the frequency or the proportion will be reported.

Primary Aim: The primary aim is demonstrating the benefit of C7, as measured by a change in performance on the primary attention measure for each age group. The proportion of subjects who achieved favorable outcome will be estimated along with the corresponding 95% confidence interval using an exact binomial method. We will also investigate if there will be significant differences in the proportions of favorable outcomes among three age groups using Fisher's exact test. We will make every effort to minimize the missing data. We expect minimal amount of missing data. If missing data occurs, missing data will be imputed using multiple imputation techniques.

Generalized estimating equation (GEE) analysis will be used to examine if C7 positively affects other neuropsychological (e.g., IQ, language, processing speed) and neurological performance, such as ataxia over time (baseline, 6 months, and 9 months).

Secondary Aim: A secondary aim is to evaluate the effect of C7 supplementation of a regular diet on an EEG activity and to evaluate the safety of C7 supplementation. EEG will be analyzed in 3 ways (spike-wave duration, total number of seizures and background of the EEG as described above). GEE analysis will be used to examine if there are significant changes in EEG activity and safety over time. GEE analysis will be also conducted to investigate whether attention neuropsychological scores correlate with the EEG findings.

Study end. Statistical analyses at the end of the study will examine the initial measures at baseline, 6 months, and 9 months. Repeated measurement data will be analyzed using the generalized estimating equation (GEE) approach. The GEE method has been widely used for the analysis of repeated measurement data because of its robustness to random missing and misspecification of the true correlation structure.

SAS V9.4 (SAS Institute, Inc. SAS V9.4, Cary, NC, 2014) will be used to analyze the data.

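### The planned GEE of attention on EEG does not separate within-patient change from between-patient severity or the on-oil shift, so run as written it does not show whether EEG reduction goes with attention gain

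*Combined protocol and SAP*

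**What the plan says.** Section 9.5 (Data Analyses, secondary aim) states: "GEE analysis will be also conducted to investigate whether attention neuropsychological scores correlate with the EEG findings". On the data, the same section says "Statistical analyses at the end of the study will examine the initial measures at baseline, 6 months, and 9 months", and on the method, "Repeated measurement data will be analyzed using the generalized estimating equation (GEE) approach". For this model it names no visit or on-oil term, covariate, change score, working correlation, or separation of within-patient from between-patient variation.

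The purpose is given in section 9.1, in the paragraph on the meaning of the EEG outcome. It argues that the expected fall in spike-wave burden after C7 may matter medically, leaves the definitive answer to later-phase trials, and for that reason says the investigators will "relate attention scores (primary outcome) with EEG recordings (used here as a surrogate marker of the disease" and a secondary outcome).

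The protocol expects both measures to move on treatment. Section 9.2.1.1: "Subjects receiving C7 supplementation will experience a significant (0.5 SD) improvement in performance on the primary attention measure". Section 9.2.2.1 expects EEG benefit "as measured by a decrease in abnormal EEG activities as defined above both in the acute and long-term", without giving a size. There is no control arm (section 9.1: "In the proposed single-arm phase II trial").

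**The concern.** EEG is a time-varying covariate here. A GEE with EEG as its only regressor estimates a single slope, fed by three sources:

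- **Severity.** Patients with worse EEG may have worse attention at every visit, whatever the treatment does. Sections 2.1 and 9.1 both note that attention is commonly impaired in seizure disorders.
- **Common shift.** Anything that moves both measures at the 6-month visit enters the slope, even if the patients whose EEG improved most are not those whose attention improved most. With one arm, this includes practice and time effects.
- **Within-patient link.** This is whether a patient's attention rises when that patient's EEG improves.

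The section 9.1 argument starts from EEG reduction after C7, so the third source is the one that answers it. A significant blended slope could be carried into the next trial as support for EEG as a marker of treatment benefit when only the first or second source is present. The robustness of GEE to a wrong correlation structure, which section 9.5 cites, protects the standard error. It does not change what the coefficient means.

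**Working it through.** **The plan's figures.** No figure is stated for this analysis; the sample size comes from the primary design in section 9.3. That design (stop at 4/7 or fewer, reject at 8/13 or fewer, 50% against 80%) reproduces: exact type I error 0.0992, power 0.818. It gives 13 evaluable patients per age group, 3 x 13 = 39 (45 recruited).

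**Inputs.**
- From the documents: N = 39 (and 45); three visits, with oil at the second only; attention shift s = 0.5 SD (section 9.2.1.1). The ICC range 0.57-0.87 is bracketed by two retest figures in section 6.3.9: K-CPT 2 (.57) and WPPSI-IV WMI (.87).
- Assumed: the same ICC for EEG; an EEG shift equal to the attention shift (0, 0.3, 0.5 SD); severity correlation of size r = 0, 0.3 or 0.5 (worse EEG with worse attention). The true within-patient association is set to zero.

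**What the EEG-only slope estimates.** Scale each measure to variance 1 before the shift. The on-oil indicator (0, 1, 0) has variance (1/3)(2/3) = 2/9 over visits. Under an independence working correlation,

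slope = -(r x ICC + (2/9)s²) / (1 + (2/9)s²).

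At ICC 0.7, with (2/9)(0.25) = 0.0556:
- severity 0.5, no shift: -(0.5 x 0.7) = -0.35 (simulated -0.35);
- shift 0.5 SD, no severity: -0.0556/1.0556 = -0.053 (simulated -0.051 to -0.058);
- both: -(0.35 + 0.0556)/1.0556 = -0.384 (simulated -0.38).

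An exchangeable working correlation gives within-patient contrasts more weight. The severity part shrinks (-0.16 to -0.17) and the shift part grows (-0.14 to -0.15). None of these slopes contains any within-patient link.

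**Share of simulated trials with a significant EEG coefficient** (two-sided 5%, robust errors, 2,000 trials per setting, ICC 0.7, N = 39 to 45):

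| Severity | Shift (SD) | EEG only, independence | EEG only, exchangeable | Visit terms added, independence / exchangeable | Within-patient term, with visit terms |
|---|---|---|---|---|---|
| 0 | 0 | 7% | 6-7% | 6-7% / 5-7% | 5-6% |
| 0.5 | 0 | 82-85% | 42-45% | 80-84% / 41-43% | 5% |
| 0 | 0.5 | 9-10% | 38-40% | 6% / 5-6% | 5-6% |
| 0.3 | 0.3 | 45-49% | 37-42% | 36-40% / 15-18% | 4% |
| 0.5 | 0.5 | 90-94% | 90-93% | 78-83% / 37-43% | 6% |

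Visit terms alone remove the shift but leave severity.

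**Over ICC 0.57-0.87** (N = 39, 400 trials per setting):
- severity 0.3-0.5 alone: about 37-90% (independence), 18-55% (exchangeable);
- shift 0.5 SD alone: 7-12% and 27-90%, the exchangeable figure rising steeply with ICC;
- within-patient term with visit terms: about 5-10%. Rates above 5% reflect uncorrected sandwich errors with few patients.

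**Cost in power.** With a true within-patient slope of -0.30 (correlation -0.30/√1.09 = -0.29), severity 0.5, shift 0.5 SD and ICC 0.7, the split model estimates -0.30 with 68% power at N = 39. The EEG-only models give -0.46 to -0.47. In separate runs, power was about 76% at a within-patient correlation of -0.3 and 42% at -0.2.

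**The case against.** The strongest reply is that this is an under-described exploratory analysis, not a wrong one. No equation is printed, and a sensible analyst might add visit terms or use change scores. Section 9.1 calls EEG a marker of the disease, and for a disease marker a between-patient association is a legitimate finding. Several stronger readings do fail:

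- A reader might infer that the plan prescribes pooling of all visits. It does not say so; that is what a repeated-measures GEE of scores on EEG findings yields by default.
- A reader might take all the percentages above as false-positive rates. The severity-only figures are not: a between-patient association exists in those runs and the model detects it. They become errors only when read as change tracking change.
- A reader might infer that raw working-memory and continuous-performance scores will be mixed. Section 9.1 already defines improvement in normative SDs. What is missing is a statement of scale and direction for this model.
- A reader might fear that this trial would establish EEG as a surrogate. Section 9.1 leaves the definitive implications to later trials.

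What the reply does not remove is that the text motivating the analysis concerns EEG reduction after treatment. Neither working correlation, nor unstated visit terms, isolates the matching coefficient. This is therefore more than missing detail.

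**Conclusion.** The point holds as stated in the heading. Run as written, the GEE gives one blended coefficient that does not answer the question raised in section 9.1. The mechanism follows from the algebra and does not depend on the simulation settings.

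The size does depend on them. The severity correlation and the EEG shift are assumptions, and the result varies strongly with ICC and working correlation. The rates show what could happen and do not forecast this trial. The shift problem is small under independence and can be large under exchangeable; the severity problem runs the other way.

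The reach is limited. A reader might infer a threat to the go/no-go decision, but that rests on the proportion of attention responders (sections 9.1 and 9.3). The rule for intermediate results refers to the other outcomes, tolerability and safety without naming this correlation, which has no decision rule of its own. It should be corrected before analysis as a secondary-analysis point.

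**What to change.** In section 9.5, write out the model:

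- Enter EEG as two terms: each patient's mean over visits, and each visit's deviation from that mean.
- Add visit and age-group terms, and name the working correlation.
- Enter attention as a normative z-score, oriented so that higher is better.
- Report the within-patient coefficient as the answer on whether EEG change tracks attention change. Report the between-patient coefficient separately, as a severity association.
- Use a small-sample correction to the sandwich standard errors.

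A change-on-change analysis would be an acceptable alternative.

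This needs a few sentences in section 9.5 and a few lines of code, on data already collected. The statistical cost should be stated alongside it. Power for the within-patient term is moderate, about 70-80% at a within-patient correlation of -0.3 and lower for weaker links. Visit terms also remove the average on-oil change, so the coefficient tests only individual variation around that average. A null result would be weak evidence against a link.

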5. STUDY INTERVENTIONS

5.1. Interventions, Administration, and Duration

5.1.1. Triheptanoin: A triglyceride oil containing three odd-carbon chain-length fatty acids (i.e., a triglyceride of 7-carbon heptanoic acid) manufactured for food applications. Triheptanoin will be taken 4 times per day (approximately every 6 hours: prior to breakfast, lunch and dinner and a mid-afternoon snack) by mouth. It is dosed 4 times per day, divided evenly. Subjects will receive supplementation at the maximum tolerable dose (MTD) determined in Protocol 1 (either 35%, 40%, or 45% of daily caloric intake). Subjects who experience acute gastrointestinal distress (nausea, mild stomach upset, mild diarrhea) may decrease the dose to 50% for two days, then increase the dose over the course of less than a week (in a manner similar to what is described in Protocol 1) until they reach the intended dose. Subjects who are unable to tolerate the maximum tolerable dose will be discontinued from the study. The oil

should be taken approximately one hour before meals, and will be mixed with fat-free, sugar-free yogurt or pudding for administration.

- 5.1.2. Forty-five subjects will be enrolled in a 6 month on/3 month off treatment trial of triheptanoin. Initiation of triheptanoin will be done in the Children's Medical Center Dallas Epilepsy Monitoring Unit.
- 5.1.3. Subjects will not be required to stop other medications. Subjects will be directed to maintain their usual medications, including rescue seizure medications, as necessary for the course of the study. Subjects may have any clinical medical records transferred back to their referring physician at completion of the study.

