9.3. Sample Size and Accrual

We estimated the sample size using the primary outcome (attention) for each of three age groups. The same method will be applied for sample size estimation in each of three age groups. An improvement of 0.5 SD or more on the primary attention measure

after the administration of C7 is considered a favorable outcome. This study will yield data that allow a clear go/no-go decision regarding whether C7 should proceed to an efficacy trial: If a favorable outcome occurs in less than 50% of subjects, we will recommend that C7 not proceed to an efficacy trial. If a favorable outcome occurs in at least 80% of subjects, we will recommend that C7 proceed to an efficacy trial.

The sample size was estimated using Simon's optimal two-stage design (24). The null hypothesis that the proportion of favorable outcome is 50% will be tested against a one-sided alternative hypothesis that the proportion of favorable outcome is 80%. In the first stage, 7 subjects will be accrued. If there are 4 or fewer favorable outcomes in these 7 subjects, the study will be stopped, and we will recommend that C7 not proceed to an efficacy trial. Otherwise, 6 additional subjects will be accrued for a total of 13 subjects. If 8 or fewer favorable outcomes are observed in 13 subjects by the end of stage two, then no further investigation of C7 is warranted. This design yields a type I error rate of 0.1 and power of 80% when the true favorable outcome occurs in 80% of subjects. We plan to recruit 15 subjects with an expected 15% dropout rate resulting in 13 subjects for each age group. That is, we will recruit a total of 45 subjects for this protocol.

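### Section 9.5 credits GEE with robustness that holds only under MCAR, and leaves unstated the choices that decide its validity under MAR and its small-sample error

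*Combined protocol and SAP*

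**What the plan says.** Section 9.5 applies GEE to the secondary aims in three places:

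- Neuropsychological and neurological outcomes: "Generalized estimating equation (GEE) analysis will be used to examine if C7 positively affects other neuropsychological" and neurological performance.
- EEG and safety: "GEE analysis will be used to examine if there are significant changes in EEG activity and safety over time".
- End of study: "Statistical analyses at the end of the study will examine the initial measures at baseline, 6 months, and 9 months", and "Repeated measurement data will be analyzed using the generalized estimating equation (GEE) approach". The reason given is "because of its robustness to random missing and misspecification of the true correlation structure".

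For these analyses the section states no working correlation, link, variance estimator, test statistic, reference distribution or significance level. It does not say whether they are pooled or run within age groups.

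Missing data are covered by one sentence in the Primary Aim paragraph: "If missing data occurs, missing data will be imputed using multiple imputation techniques". It gives no imputation model and does not say whether imputed data enter the GEE.

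On numbers, section 9.3 says: "We plan to recruit 15 subjects with an expected 15% dropout rate resulting in 13 subjects for each age group". That makes 45 recruited in total.

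On exits, section 5.1.1 says: "Subjects who are unable to tolerate the maximum tolerable dose will be discontinued from the study". Further routes out are in section 5.3.3 (failure to return to the required dose), section 6.2.2.2 (a clearly worse local EEG), section 7 (continued weight gain) and section 8 (laboratory findings, non-compliance). Section 6.3.9 expects that some subjects will be too impaired to give usable test scores.

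**The concern.** The justification joins two properties that unweighted GEE does not have together under MAR. The estimating equations stay unbiased with a wrong working correlation only if missingness is MCAR. If missingness depends on observed values, validity requires a near-correct working correlation, weighting or imputation.

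MCAR is doubtful here. One exit route follows a worse EEG, and EEG is itself a GEE outcome. Unusable scores are expected in the most impaired subjects.

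The second issue is size. The usual sandwich covariance is a large-sample result, and a Wald test built on it rejects too often with few subjects. This trial has at most 45.

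The secondary outcomes carry weight. Under section 9.1, if an intermediate share of subjects (51% to 79%) respond, the remaining outcomes help settle the go/no-go decision. In an open-label single-arm trial, leaving working correlation, variance estimator and reference distribution open also lets them be chosen after the data are seen.

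**Working it through.** **Inputs from the documents.** Three time points (baseline, 6 and 9 months; 9.5). Fifteen recruited and 13 evaluable per age group, 15% dropout (9.3). Pooled totals are 3 × 15 = 45 and 3 × 13 = 39.

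**Assumptions not in the documents.** Two-sided 5% level for secondary tests, within-subject correlation 0.5 to 0.85, logistic dropout slopes of 0.5 to 2 per SD, and gamma-Poisson counts.

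**The plan's own figures.** There is no stated error rate or power for the GEE. The primary design reproduces. With stopping at 4 or fewer of 7, and failure at 8 or fewer of 13, the exact type I error at a 50% response rate is 0.0992 (stated 0.1). Power at 80% is 0.818 (stated 80%).

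**1. Size of an uncorrected sandwich Wald test, complete normal data.** With identity link and a saturated time effect, the sandwich variance is the sample variance of the within-subject differences with divisor n.

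- One contrast: size = P(|t| > 1.96 × √((n−1)/n)), with n−1 degrees of freedom.
- Two-df time test: size = P(F(2, n−2) > 5.9915 × (n−2)/(2n)) = (1 + 5.9915/n)^(−(n−2)/2).

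| n | t cut-off | One contrast | 2-df test |
|---|---|---|---|
| 45 | 1.938 | 5.9% | 6.8% |
| 39 | 1.935 | 6.05% | 7.1% |
| 15 | 1.894 | 7.9% | 11.3% |
| 13 | 1.883 | 8.4% | 12.4% |

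Example, 2 df at n = 39: (1 + 0.1536)^(−18.5) = 0.071.

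Simulation agrees with these values. In the same simulations, t and Hotelling F references gave 4.8% to 5.2%. A 2-df score test gave 3.4% at n = 13 and 4.7% at n = 45, so it is not liberal.

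**2. Incomplete data and counts.** GEE was fitted with exchangeable working correlation and 15% random dropout, 1,000 runs per row. Counts had mean 20 with gamma variation between subjects and between visits.

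| Outcome | n | One contrast | 2-df test | One contrast, Mancl-DeRouen with t |
|---|---|---|---|---|
| Normal | 13 | 9.6% | 15.8% | 3.8% |
| Normal | 45 | 5.3% | 6.5% | 4.2% |
| Counts | 13 | 16.9% | 27.7% | 9.9% |
| Counts | 45 | 8.5% | 12.7% | 7.3% |

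The correction holds the level for normal outcomes. For skewed counts it helps but leaves an excess.

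**3. Bias under MAR dropout with no true change.** Suppose dropout depends on the baseline score. With an independence working correlation, the later mean is then the raw mean of those who remain. Its expected value is correlation × mean baseline score of those who remain. With 15% dropout concentrated in low scorers, that baseline mean is 0.07, 0.13, 0.18 and 0.20 SD for slopes of 0.5, 1, 1.5 and 2 per SD.

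- Correlation 0.6, slopes 0.5 to 1.5: 0.6 × 0.07 = 0.04 up to 0.6 × 0.175 = 0.105 SD.
- Correlation 0.5 to 0.85, slopes 1 to 2: 0.5 × 0.13 = 0.07 up to 0.85 × 0.20 = 0.17 SD. Large-sample simulation gives 0.06 to 0.17 SD.
- Exchangeable working correlation, same simulated data: at most about 0.02 SD.
- MCAR: no bias.

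The unnamed working correlation therefore decides whether a spurious change appears.

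**The case against.** Several points on the other side are sound.

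- **The robustness sentence may be correct.** If random missing means MCAR, it is. The fault is then an undefined term whose assumption fits the exit rules poorly.
- **Multiple imputation is planned.** Its wording is general, and imputation followed by GEE can be valid under MAR. A reader might infer that MAR is unhandled. The documents support only that the reach of the imputation is unclear.
- **Stopping treatment is not the same as having no data.** Section 6.2.3 asks early leavers to return for neuropsychological testing and a fasting EEG, and section 8 asks for a final visit. The bias calculation treats the 15% as plain dropout and assumes that low scorers leave. The documents do not tie intolerance, laboratory findings or non-compliance to test scores.
- **Uncorrected standard errors are not stated.** A reader might infer them, but section 9.5 is silent on variance and test.
- **Age-group GEE is not stated.** A reader might take 8% to 12% as the error of the planned tests. Section 9.5 mentions age groups only for the primary attention measure, so pooling is the natural reading.
- **No significance rule governs the intermediate zone.** Section 9.1 weighs impact on the other outcomes, with tolerability and safety, so excess test error does not pass mechanically into the decision.

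These points narrow the size of the problem. They do not supply the missing specification. The pooled figures also assume that all three age groups accrue fully. If each stopped after 7 subjects, n would be 3 × 7 = 21, and the same formulas give 7.0% and 9.2%.

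**Conclusion.** The concern holds as a misstated justification and a specification gap in the secondary analyses. Joint robustness to missingness and to a wrong correlation structure can be claimed only under MCAR, which this protocol makes doubtful. Under MAR, what protects the analysis is a working correlation, weighting or imputation step that section 9.5 does not specify for the GEE.

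If a standard sandwich Wald test is used, the excess error is about 1 to 2 percentage points for normal outcomes in the pooled analysis. It is larger for skewed counts, at about 8.5% to 13% with 45 subjects. That figure rests on the assumed overdispersion. The 8% to 12% range applies only to analyses within age groups of 13 to 15.

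The bias of 0.04 to 0.17 SD shows what independence GEE could do under assumed score-related dropout. It is not a prediction for this trial. At its largest it is about a third of the 0.5 SD response threshold (0.17/0.5 = 0.34), and a near-correct correlation structure almost removes it.

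The primary Simon design and its exact binomial interval are unaffected.

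**What to change.** In section 9.5:

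1. Restrict the robustness claim to MCAR, and state the missingness assumption for each analysis.
2. Analyse continuous secondary outcomes with a likelihood-based repeated-measures model, visit as a category, and Kenward-Roger degrees of freedom. Include early-exit assessments where available, and say how they are assigned to visits.
3. Where GEE is kept, for example for EEG counts, name a working correlation other than independence. State that multiple imputation or weighting feeds it, with the model. Use a small-sample-corrected covariance (such as Mancl-DeRouen) with a t or F reference.
4. State whether each analysis is pooled or by age group, and at what level it is tested.
5. Record two limits. The correction is incomplete for skewed counts (7.3% at 45 subjects in the simulation above). Neither approach cures missingness not at random, which could arise if exit follows a local EEG that is not in the trial dataset, so results should be read with that in mind.

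The cost is SAP wording and different options in the same SAS package, with slightly larger p-values. No extra subjects or assessments are needed.
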